#### **11.1.1.1. Number of tender joints/swollen joints**

The number of tender joints and number of swollen joints will be assessed, with a total of 68 joints assessed for tenderness, and 66 assessed for swelling. This assessment is performed independently of the assessment of 28 tender/swollen joints for the DAS28.

Descriptive statistics for actual value and change from baseline for both the number of tender joints and the number of swollen joints will be presented for the efficacy population, efficacy – 2nd treatment course in Main Study Period subset and efficacy – Extension Study Period subset by treatment group at each visit. A listing will be provided for the all-randomized population by treatment group and visit, showing number of tender and swollen joints at each visit, along with the percentage change from baseline.

#### **11.1.1.2. Visual Analogue Scale (VAS)**

The VAS ranges from 0 to 100 mm, with higher scores indicating poorer status or more severe pain. A VAS is used to record the Patient Assessment of Pain, the Patient Global Assessment of Disease Activity, and the Physician Global Assessment of Disease Activity at every visit where an efficacy assessment is performed.

For these scales, descriptive statistics for actual value and change from baseline will be presented for the efficacy population, efficacy – 2nd treatment course in Main Study Period subset and efficacy – Extension Study Period subset by treatment group at each visit. Additionally, the Patient and Physician Global Assessment of Disease Activity will be summarized at each visit. A listing will also be provided showing VAS measurements at each visit, along with the percentage change from baseline by treatment group and visit in all-randomized population.

#### **11.1.1.3. Health Assessment Questionnaire (HAQ) Estimate of Physical Ability (HAQ Disability Index)**

The arthritis-related functional disability will be measured using the disability index of the HAQ, a validated, self-administered form that assesses functional ability in a number of relevant areas, including the ability to dress, rise from bed, eat, walk, maintain personal hygiene, reach, grip, and other activities on a scale ranging from 0 (no difficulty) to 3 (unable to perform the activity). Scores range from 0 to 3, with higher scores indicating worse disability.

There are 8 categories within the Health Assessment Questionnaire:

- Dressing and Grooming (Questions 1, 2)

- Arising (Questions 3, 4)
- Eating (Questions 5, 6, 7)
- Walking (Questions 8, 9)
- Hygiene (Questions 10, 11, 12)
- Reach (Questions 13, 14)
- Grip (Questions 15, 16, 17)
- Activities (Questions 18, 19, 20)

The answer to each question will be scored as follows: Without any difficulty = 0, With some difficulty = 1, With much difficulty = 2, Unable to do = 3.

In order to compute the disability index:

(1) Obtain a score for each category by taking the highest score recorded from the questions within the category. The maximum score is taken regardless of missing values in questions, i.e. at least one question must have an assigned score. If all questions have missing values, the score is recorded as missing.

(2) Adjust each category for use of aids/devices and/or help from another person using the tables below. If the score for a category is 0 or 1 after step 1, and any of the aids/devices/help from another person fields are marked, the score should be increased to 2. If a patient's highest score for that category is 2 already, it remains 2, and if 3 already, it remains 3.

**Table 3: Aids/Devices Items for HAQ Categories**

Item	HAQ Category
Devices used for dressing (button hook, zipper pull, long handled shoe horn, etc.)	Dressing & Grooming
Special or Built up chair	Arising
Built up or special utensils	Eating
Cane	Walking
Walker	Walking
Crutches	Walking
Wheelchair	Walking
Raised toilet seat	Hygiene
Bathtub seat	Hygiene
Bathtub bar	Hygiene
Long handled appliances in bathroom	Hygiene
Long handled appliances for reach	Reach
Jar opener (for jars previously opened)	Grip

Note: The assignment of devices to particular disability categories assumes that the devices are used only for their intended purposes.

**Table 4: Help from another Person Items for HAQ Categories**

Item	HAQ Category
Dressing & Grooming	Dressing & Grooming
Arising	Arising
Eating	Eating
Walking	Walking
Hygiene	Hygiene
Reach	Reach
Gripping and opening things	Grip
Errands and chores	Activities

(3) A minimum of 6 categories must have a score assigned in order for the HAQ estimate of physical ability to be derived. If there are only scores available for less than 6 categories, the HAQ estimate of physical ability cannot be computed and should be recorded as missing. If there are 6 or more categories with a score assigned, divide the summed category scores by the number of categories answered to obtain the HAQ estimate of physical ability.

Descriptive statistics for actual value and change from baseline of the HAQ estimate of physical ability will be presented for the efficacy population, efficacy – 2nd treatment course in Main Study Period subset and efficacy- Extension Study Period subset by treatment group at each visit. A listing will be provided showing the patient’s score for each category and HAQ estimate of physical ability. Listings will also be provided showing the raw scores for each question, the responses to the “Aids/Devices” categories, and the “Help from Another Person” categories. These listings will all be displayed in all-randomized population by treatment group. This assessment comprise of a VAS on a scale of 0 to 100, in cases where the length of the VAS is not 100mm the score is converted into a 0 to 100 range in clinics. This scale will be listed by treatment group and visit.

**11.1.1.4. C-Reactive Protein and Erythrocyte Sedimentation Rate**

Descriptive statistics for actual value and change from baseline will be presented for both C-reactive protein (CRP) and erythrocyte sedimentation rate (ESR) by treatment group at each visit for the efficacy population, efficacy – end treatment course in Main Study Period subset and efficacy – Extension Study Period subset. Note that CRP and ESR will also be summarized for the pharmacodynamic population by treatment group, and this is described in the pharmacodynamics section.

Separate listings will be provided for each of these parameters which will show the measurements at each visit, along with the percentage change from baseline, by treatment group in all-randomized population.

**11.1.1.5. Joint Surgery**

A listing will be produced displaying for patients undergoing any surgical joint procedure (including bone or joint surgery or synovectomy (including joint fusion or replacement)). That

will display the surgical procedure performed (as coded by MedDRA version 18.1 or higher) and the procedure date.

#### **11.1.2. Time to Onset of ACR20**

Time to onset of ACR20 response (in days) will be summarized by treatment group for the efficacy population up to Week 24. Patients not achieving the ACR20 response will be censored using the last time point where the ACR was assessed. Duration will be calculated as [date of event (onset of ACR20 response) or date censored (last assessment for which ACR20 responder status can be determined) – date of randomization + 1]. Kaplan-Meier estimates of the 25th percentile, median, and 75th percentile of time to onset will be presented. Also, p-value calculation from log-rank test between CT-P10 and Rituxan + MabThera group will be provided. In the event that there are not enough patients with an ACR20 response for these statistics to be produced, the result will be recorded as not estimated (N.E.). The number and percentage of patients with ACR20 response during the 24 weeks will be summarized. A listing will be provided showing time to onset of ACR20 response (in days) for each patient in the all-randomized population, by treatment group.

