**Figure 1: Study Schematic**

\* The third course of treatment will be initiated between Week 48 and Week 52 of the Entire Study Period based on the results assessed within 8 weeks from the Extension Week 0.

Any courses of treatment after the first course will be initiated if the following safety criteria are met:

- Absolute neutrophil count should be  $\geq 1.5 \times 10^3$  cells/ $\mu$ L (SI units:  $\geq 1.5 \times 10^9$  cells/L), platelet count should be  $\geq 75 \times 10^3$  cells/ $\mu$ L (SI units:  $\geq 75 \times 10^9$  cells/L), aspartate aminotransferase or alanine aminotransferase should be  $\leq 2.5$  times the upper limit of normal and levels of IgG should be  $\geq 500$  mg/dL (5.0 g/L), at the last blood sample analysis (i.e. Week 16 for second course of treatment and within 8 Weeks from the Extension Week 0 for third course of treatment).
- The patient has not developed any conditions which, in the investigators opinion, would preclude the patient receiving further courses of treatment (e.g., any new or uncontrolled disease such as, but not limited to, cardiovascular disease, or nervous system, pulmonary, renal, hepatic, endocrine, or gastrointestinal disorder).

[figure not shown]
Note that Part 1 and Part 2 of the study will follow the study schematic specified in [Figure 1](#).

In Part 1, the first approximately 189 patients with RA will be randomly assigned in a 1:1:1 ratio to 1 of 3 treatment groups, CT-P10, Rituxan, or MabThera (approximately 63 patients per treatment group).

In Part 2, approximately 172 subsequent patients with RA will be randomly assigned in a 1:1 ratio to 1 of 2 treatment groups, CT-P10 or Rituxan. In total, approximately 361 patients will be available for analysis.

Approximately 189 initial patients to be enrolled in the study will be assigned to Part 1 and all subsequent patients enrolled in the study will be assigned to Part 2. All patients from Part 1 of the study will be included in Part 2 of the study and undergo all assessments performed in Part 2. A schematic of study patient assignment for Part 1 and Part 2 is presented in [Figure 2](#). Part 2 will run independently and in parallel with Part 1.

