### 5.2. Sample Size

For Part 1, 189 patients will be randomized in a 1:1:1 ratio to the CT-P10, Rituxan, and MabThera groups. Later, for Part 2, 172 patients will be allocated in a 1:1 ratio to the CT-P10 and Rituxan groups.

Part 1 of this study is powered to demonstrate PK similarity of CT-P10, Rituxan, and MabThera in  $AUC_{0-last}$ ,  $AUC_{0-\infty}$ , and  $C_{max}$ . Similarity will be demonstrated if the 90% confidence interval (CI) for the geometric mean ratio of CT-P10 to Rituxan and MabThera in  $AUC_{0-last}$ ,  $AUC_{0-\infty}$ , and  $C_{max}$  is within the bounds of 80% and 125%.

In Part 1, based on overall 90% power, Two one-sided alpha equal to 0.05, an interpatient CV in  $AUC_{0-last}$  of 30%, and a true of geometric mean equal to 1, fifty patients are needed in each treatment group being compared (50 patients in the CT-P10 treatment group, 50 patients in the MabThera treatment group, and 50 patients in the Rituxan treatment group: 150 patients total). The statistical power of each comparison, CT-P10 versus MabThera, CT-P10 versus Rituxan,

and MabThera versus Rituxan is 96.5% to achieve overall 90% power accounting for multiplicity with type II error correction. Allowing for a drop-out rate of 20%, 189 patients will be randomly assigned into the study in a 1:1:1 allocation.

In Part 2, the sample size of 322 evaluable patients (133 patients in the CT-P10 group and 189 patients in the reference products group [Rituxan and MabThera groups]) leads to approximately 90% power for the demonstration of similarity based on a two-sided 90% CI for the difference of mean change of DAS28 (CRP) score at Week 24 from baseline value between CT-P10 and reference products for an equivalence margin of  $\pm 0.50$ . In this sample size calculation, the common standard deviation of the mean change of DAS28 at Week 24 from baseline is assumed as 1.32 based on the CT-P10 1.1 study result for the therapeutic equivalence margin of  $\pm 0.50$ . Incorporating hypothesized drop-out rate of 10%, total sample size of 361 subjects (149 eligible patients in the CT-P10 and 212 eligible patients in the reference products group, including up to 63 patients from each of the CT-P10, Rituxan, and MabThera groups in Part 1) will be used in evaluation of efficacy endpoints.

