**Table 1: Populations and Subsets of Analysis**

Populations	Subsets
Main Study Period: Part 1	
all-randomized	
safety	
pharmacokinetic	pharmacokinetic (antibody negative subset) pharmacokinetic (antibody positive subset)
Main Study Period: Part 2	
all-randomized	all-randomized (antibody negative subset)
safety	safety – 2 nd treatment course in Main Study Period subset
efficacy	efficacy (antibody negative subset) efficacy (antibody positive subset) efficacy – 2 nd treatment course in Main Study Period subset
pharmacokinetic	pharmacokinetic (antibody negative subset) pharmacokinetic (antibody positive subset) pharmacokinetic – 2 nd treatment course in Main Study Period subset
pharmacodynamic	pharmacodynamic (antibody negative subset) pharmacodynamic – 2 nd treatment course in Main Study Period subset
Extension Study Period	
all-randomized	all-randomized – Extension Study Period subset
safety	safety – Extension Study Period subset
efficacy	efficacy – Extension Study Period subset
pharmacodynamic	pharmacodynamic – Extension Study Period subset

All-randomized, safety and PK populations and its subsets will be defined for the patients from Part 1 and 2, respectively. Efficacy and PD population and its subsets will be defined for the Part 2. Population for Part 2 will include patients from Part 1.

Patients who have any major protocol deviations (as defined in [Section 5.6](#)) may be excluded only from the population (PD and/or Efficacy) that would be affected by the deviation. Patients from the significant GCP non-compliance sites as defined in [Section 5.6](#) will be excluded in all populations.

The number of patients in all populations will be tabulated by the treatment group in each relevant Part and study period. A listing will also be produced, displaying this data.

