### 11.2. DAS28

The ANCOVA comparing the change from baseline of DAS28(CRP) and DAS28(ESR) at 24 weeks of treatment between two treatment groups, CT-P10 and combined Rituxan and MabThera group will be analyzed, considering the treatment as a fixed effect and gender, country, race, study part, interaction of treatment group with study part, prior anti-TNF- $\alpha$  blocker status (intolerance case versus inadequate response), and RF or anti-CCP status (both positive versus both negative versus either RF or anti-CCP negative) fitted as covariates. Clinically relevant variables at baseline are used as the covariates for adjusted means. If country is found to be unsuitable as a covariate due to the number of levels, then region (EU, non-EU), which may pool countries based on continents, may be used instead. Additional ANCOVA will be conducted in patients whose ADA status result at Week 24 is “Negative”.

The least squares mean and corresponding standard error of the change from baseline in DAS28 at Week 24 will be presented for each treatment group. Point estimates (least squares mean and difference of least squares means), 90% confidence interval (CI) for the treatment difference and p-value with an interaction effect between study part and treatment group will also be provided. When there are Significant GCP non-compliance sites, an additional sensitivity analysis will be performed.

All-randomized population and efficacy population will be used for analysis of change from baseline of DAS28 (ANCOVA), respectively.

Descriptive statistics for actual value and change from baseline in disease activity measured by DAS28 (CRP) and DAS28 (ESR) will be summarized at each visit for the efficacy population, efficacy – 2nd treatment course in Main Study Period subset and efficacy – Extension Study Period subset by treatment group. Descriptive statistics for actual value and change from baseline in DAS28 (CRP) and DAS28 (ESR) in patients whose swollen joints (of 66 assessed) and tender joints (of 68 assessed) equal to or higher than 8 at baseline at each visit will be also summarized for the efficacy population, efficacy – 2nd treatment course in Main Study Period subset and efficacy – Extension Study Period subset. In addition, descriptive statistics of DAS28 at each visit will be summarized for the Efficacy (Antibody Negative/Positive Subset).

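### The log-rank test for time to ACR20 onset (SAP 11.1.2) pools two Parts with different allocation ratios and is not stratified by study part

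*SAP*

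**What the plan says.** SAP 11.1.2 sets the population and follow-up: "Time to onset of ACR20 response (in days) will be summarized by treatment group for the efficacy population up to Week 24". It plans Kaplan-Meier quartiles for each group and adds that a "p-value calculation from log-rank test between CT-P10 and Rituxan + MabThera group will be provided". No stratification factor or covariate is named. Protocol 7.8.2.2 asks only for a summary of this endpoint by treatment, so the p-value is an addition made in the SAP.

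The efficacy population pools both Parts. SAP 5.4 (Table 1) says: "Population for Part 2 will include patients from Part 1". The Parts were randomized at different ratios. SAP 5.2 says "For Part 1, 189 patients will be randomized in a 1:1:1 ratio to the CT-P10, Rituxan, and MabThera groups" and then "for Part 2, 172 patients will be allocated in a 1:1 ratio to the CT-P10 and Rituxan groups", giving "149 eligible patients in the CT-P10 and 212 eligible patients in the reference products group". SAP 4.1 confirms that Part follows enrolment order: after the first 189 or so patients, "approximately 172 subsequent patients with RA will be randomly assigned in a 1:1 ratio to 1 of 2 treatment groups, CT-P10 or Rituxan".

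Elsewhere the SAP models Part explicitly. The Week 24 DAS28 ANCOVA in SAP 11.2 includes "study part, interaction of treatment group with study part". The imputation and tipping-point models (SAP 5.8) and the PD models (SAP 12.2) carry the same terms.

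**The concern.** Within each Part the comparison is properly randomized. Pooling Parts with different allocation ratios, without conditioning on Part, breaks that. The reference group is weighted toward early enrolment, and the CT-P10 group toward late enrolment. If response rates drift between the two periods, for example because countries or case mix change, part of the drift shows up as a treatment effect. If Part 1 patients respond faster, CT-P10 looks slower; if they respond more slowly, CT-P10 looks faster. The error is a directional bias, and a larger trial with the same design would not remove it.

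At stake is a reported p-value for the treatment contrast in a similarity trial. A significant result caused partly by the Part mix would have to be explained beside the equivalence conclusion. A non-significant result would not show similarity either, because a log-rank test of difference has no margin and no power is stated for it.

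**Working it through.** **The plan's own figures.** No power or effect size is stated for the log-rank, so the nearest checks are the group totals and the DAS28 power in SAP 5.2.

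- CT-P10: 63 + 86 = 149. Reference: 63 + 63 + 86 = 212. Total: 361. All agree with the SAP.
- DAS28 equivalence: SE = 1.32 × √(1/133 + 1/189) = 0.149. Power = 2Φ(0.50/0.149 − 1.645) − 1 = 91.1%, consistent with the stated figure of about 90%.

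**Share of each group that comes from Part 1.**

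- CT-P10: 63/149 = 42.3%.
- Pooled reference: 126/212 = 59.4%.
- Difference: 17.2 percentage points.
- With the evaluable numbers in the protocol synopsis (56 per arm from Part 1), the shares are 56/133 = 42.1% and 112/189 = 59.3%, so the imbalance is the same.

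**Leakage on the proportion scale.** Let D be the between-Part difference in response, with no treatment effect. The crude pooled contrast is then shifted by 0.172 × D: 1.7 points for D = 10 points, 2.6 for D = 15 and 3.4 for D = 20.

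**Effect on the log-rank.** Simulation used 3,000 trials per scenario, planned numbers (63/126 and 86/86), no treatment effect, six efficacy visits (Weeks 4 to 24), the plan's 10% dropout, constant hazard within Part and a two-sided 5% level. Assumed inputs are the Part 2 Week 24 ACR20 rate (60% or 75%) and the Part 1 : Part 2 hazard ratio (HR) for onset. The implied Part 1 rate is 1 − (1 − Part 2 rate)^HR; for example, 1 − 0.40^1.5 = 74.7%.

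| Part HR | Part 1 rate (Part 2 = 60%) | Unstratified | Stratified | Part 1 rate (Part 2 = 75%) | Unstratified | Stratified |
|---|---|---|---|---|---|---|
| 1.0 | 60.0% | 5.1% | 5.0% | 75.0% | 4.8% | 5.0% |
| 1.25 | 68.2% | 5.9% | 5.2% | 82.3% | 6.2% | 5.6% |
| 1.5 | 74.7% | 8.3% | 5.0% | 87.5% | 8.3% | 5.0% |
| 2.0 | 84.0% | 14.0% | 5.4% | 93.8% | 14.6% | 5.1% |
| 0.8 | 52.0% | 5.6% | 5.0% | 67.0% | 6.0% | 5.0% |
| 0.67 | 45.9% | 7.5% | 4.8% | 60.5% | 7.9% | 5.2% |
| 0.5 | 36.8% | 11.0% | 4.9% | 50.0% | 12.7% | 4.9% |

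The Monte Carlo standard error at 5% is √(0.05 × 0.95/3000) = 0.4 points, so the excess at a ratio of 1.25 or 0.8 is small even against simulation noise.

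The mean of the unstratified Z, in absolute value, is 0.26-0.31 at ratios 1.25 or 0.8, 0.45-0.56 at 1.5 or 0.67, and 0.74-0.95 at 2.0 or 0.5. As a cross-check, a mean of 0.52 (ratio 1.5, Part 2 rate 60%) gives Φ(−1.44) + Φ(−2.48) = 0.075 + 0.007 = 8.2%, against 8.3% simulated. The stratified Z has mean 0.011 or less in absolute value throughout.

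**The case against.** The case for leaving the text alone has real substance.

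- **The Parts may not differ.** Eligibility criteria and study scheme are common to both Parts, and the documents give no ACR20 rates by Part. This stands: the size of the inflation is conditional, and it is small for modest drift.
- **An unconfounded display exists.** SAP 5.7 shows Main Study Period results, other than ANCOVA, for CT-P10, Rituxan and MabThera separately as well as combined. CT-P10 to Rituxan is 1:1 in both Parts (63:63 and 86:86), so that pair carries no Part imbalance. This helps a careful reader, but the planned p-value is still the pooled one.
- **Nothing formal depends on it.** No alpha, margin or success rule is attached to this p-value, and neither document says that a non-significant result supports similarity. This stands, and it limits the severity.
- **Stratification may be intended.** The absence of strata is read from silence. However, the SAP names study part wherever it models it, so a programmer following SAP 11.1.2 would run the test without strata.

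Three stronger readings are tempting but unsupported. First, a reader might infer that this is the only inference on a secondary efficacy endpoint. It is not: SAP 11 lists DAS28 (ESR) at Week 24 as secondary, and SAP 11.2 gives it a Part-adjusted ANCOVA with a 90% CI. Second, a reader might infer that a Part difference appears in full as a treatment difference; only about 17% of it does. Third, a reader might extend the point to a biased pooled ACR20 difference, but SAP 11.1.1 plans proportions by group and no such contrast.

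**Conclusion.** The point holds as a limited one. Among formal between-group comparisons of secondary efficacy endpoints, the log-rank in SAP 11.1.2 is the only one that ignores study part, and the only one with a planned p-value for the treatment contrast. The 17-point imbalance in Part mix is fixed by the allocation ratios. How far it distorts the test depends on how much the Parts differ: no distortion if they are alike, type I error of about 6% at a Part hazard ratio of 1.25, 7.5-8% at 1.5 and 11-15% at 2.0, with each range including the inverse ratio. These figures assume constant hazard within Part and Week 24 response of 60% or 75% in Part 2, none of which the documents supply.

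The primary DAS28 (CRP) equivalence analysis has its own Part adjustment and is untouched. The change is worth making because it removes a bias built into the design at almost no cost, not because the trial's main conclusion is at risk.

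**What to change.** In SAP 11.1.2, state that the log-rank test of CT-P10 against the pooled reference is stratified by study part. This matches the treatment of Part in the DAS28 and PD models. It costs one sentence in the SAP and one strata statement in the program, and needs no new data.

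Optionally, report beside it the hazard ratio for ACR20 onset from a Cox model stratified by study part, with a 90% CI to match the DAS28 reporting. Label it descriptive, since no margin is defined for it, and note that a non-significant log-rank does not show similarity. This adds one model and one table row. No stratified ACR20 difference is requested.
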